12.3 Efficacy Analysis

The FAS will be used for all efficacy endpoints. Additionally, the primary and secondary endpoint analyses will also be performed on the PPS. The primary endpoint of the OS rate at 3 years as well as OS at 12 months, and CNS/LM PFS at 6 and 12 months with corresponding 95% confidence intervals, will be estimated using Kaplan-Meier methods using the FAS. The comparison to external controls (OS only) will be exploratory and performed using multiple cox regression taking into account the most important prognostic factors identifiable in the historic data. The median OS and CNS/LM time and associated 95% confidence interval will be calculated. Results will be displayed with Kaplan Meier plots. ORR according to RANO criteria and CSF cytology as well as CSF cytology alone, will be assessed, 95% confidence intervals will be calculated using the Clopper-Pearson exact methodology.

12.4 Safety Analysis

The safety analysis set will be used for all safety analyses. Adverse event data will be listed individually, and the incidence of adverse events will be summarized by system organ class (SOC) and preferred terms for each treatment group. AEs will be coded using the Medical Dictionary for Regulatory Activities (MedDRA) version 19.0 or later. AEs will be regarded as treatment-emergent adverse events (TEAEs) if they occur after first administration of ^{131}I -omburtamab. Related AEs are defined as adverse drug reactions (ADRs).

Listings will be made of all AEs, including non-TEAEs. All TEAEs, ADRs, SAEs and serious adverse reactions (SARs) will be summarized. The summaries will include number of events, number of patients, and percentage of patients reporting these events and will be tabulated by SOC and preferred term (PT). TEAEs will also be summarized by severity and by relationship to IMP. When calculating the incidence of adverse events, each adverse event will be counted only once for a given patient within a specified SOC, preferred term. If the same adverse event occurs on multiple occasions for a patient, the occurrence with the highest severity and relationship to IMP will be reported. Changes in vital signs, hematology, and clinical chemistry parameters from baseline to the end of the trial will be examined. Treatment-emergent changes from normal values to abnormal values in key laboratory parameters will be identified. Effects on cognitive functions will be assessed summarizing changes from baseline in performance testing results with descriptive statistics.

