6.1.4 Duration of treatment

A single treatment cycle will last 4 weeks and includes premedication, intracerebroventricular ^{131}I -omburtamab administration [REDACTED], an observation period, and post-treatment evaluations (see Figure 1 One ^{131}I -omburtamab treatment cycle after the interim analysis).

Figure 1 One ^{131}I -omburtamab treatment cycle after the interim analysis

[figure not shown]
Patients without Grade 4 toxicity and without objective disease progression (as determined by neurologic and/or radiographic examination) by MRI at week 4 in cycle 1 will be eligible to receive a second ^{131}I -omburtamab dosing cycle. Patients with Grade 3 toxicity will receive a second dosing cycle at the discretion of the investigator. For patients presenting with ongoing Grade 3 or 4 myelosuppression at week 4, a delay of dosing cycle 2 for up to 8 weeks can be introduced. Dose delay may be enforced at the discretion of the treating physician.

In case of a subsequent relapse in the CNS/LM during the follow-up period, re-treatment to target minimal residual disease can be considered and allowed in case the patient/parents provide written consent to this. In these cases, it is recommended that patients undergo the salvage treatment as specified in Appendix 2 before subsequent administration of ^{131}I -omburtamab. The administration of ^{131}I -omburtamab in these cases must follow the scheme of the treatment cycle as illustrated in Figure 2.

Patients who complete at least one treatment cycle will be evaluable. All patients who complete at least one treatment cycle (one dose of ^{131}I -omburtamab) will form part of the dataset. However, patients who do not continue to the second treatment cycle (for whatever reason) will be registered as “early treatment discontinuation” in the eCRF. Patients receiving both treatment

cycles of ^{131}I -omburtamab will be registered as “completed treatment” in the eCRF. All evaluable patients will first enter a follow-up period through week 26 (Figure 2) and thereafter the long-term follow-up where patients will be evaluated every half year for up to 3 years post- ^{131}I -omburtamab treatment where after the trial is ended.

)

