8.1.2 Secondary endpoints

1. CNS/LM PFS at 6 and 12 months will be estimated based on the time from first treatment dose to CNS/LM progression or death from any cause. Patients alive without CNS/LM progression at time of analysis, will be censored at last date of disease evaluation without evidence of progression.
2. OS at 12 months will be estimated based on the time from first treatment dose to death by any cause. Patients alive at time of analysis, will be censored at last date known to be alive.
3. ORR assessed as a combination of partial response and complete response as defined by the Response assessment in Neuro-Oncology (RANO) group criteria for brain metastasis (Lin et al, 2015) or leptomeningeal metastases as defined by EANO-ESMO criteria (Le Rhun et al, 2017). ORR will be assessed at 6 months after the first treatment dose of ^{131}I -omburtamab
4. ORR according to CSF cytology. Response is defined as a complete response when CSF converts from positive at baseline to negative after treatment with ^{131}I -omburtamab
5. Whole-body, organ, blood, and CSF radiation dosimetry.
6. Pharmacokinetic analysis of activity in blood and CSF including derivation of best-fit uptake and/or clearance parameters (half-times, maximum value) of time-activity concentration curves and of I-131 residence times (i.e., cumulated activity) concentrations (in $\mu\text{Ci}\cdot\text{h/g}$).
7. The frequency, type, and duration of treatment-emergent severe adverse events and serious adverse events, including clinically significant laboratory abnormalities. All adverse events will be graded according to Common Terminology Criteria for Adverse Events (CTCAE), version 4.0.
8. Performance assessment to monitor gross changes in neurological function is performed at week 26 and subsequently every 6 months during trial period.
9. The rate of ADA occurrence assessed three weeks after the first and second treatment dose of ^{131}I -omburtamab

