10.8 Reporting of Adverse Events

All events meeting the definition of an AE must be collected and reported in the eCRF. AEs occurring between Screening and first treatment must be recorded as Medical History.

SAEs and AESIs (whether serious or non-serious) should be reported both in the eCRF and on the paper clinical AE report form. SAEs must be reported from the first trial related activity after the patient has signed the informed consent until 3 weeks after last IMP administration.

Subsequent SAE reporting (occurring later than after 3 weeks after last IMP administration)

and during the long-term FU period (3 years) only SAEs considered related to the trial medication or new onset of cancers regardless of causality should be reported. The investigator should report these SAEs within the same timelines as for SAEs during the trial.

For patients withdrawn from the trial, please see section 6.9.3.

During each contact with the trial site staff, the patient must be asked about AEs, for example by asking: "Have you experienced any problems since the last contact?" All AEs, observed by the investigator or patient, must be reported by the investigator and evaluated unless specifically excluded. All SAEs and AEs leading to discontinuation of trial product either observed by the investigator or patient must be reported by the investigator and evaluated. All AEs must be recorded by the investigator on an AE form in the eCRF. The investigator should report the diagnosis, if available. If no diagnosis is available, the investigator should record each sign and symptom as individual AEs using separate AE forms. All pre-defined Adverse Events of Special Interest must be reported as SAEs.

For SAEs & AESIs, the clinical AE report form must be completed in addition to the AE form in the eCRF. If several symptoms or diagnoses occur as part of the same clinical picture, one safety information form can be used to describe all the SAEs. For all non-serious AEs, the applicable forms in the eCRF should be signed when the event is resolved or at the end of the trial at the latest.

Timelines for initial reporting of AEs:

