10.9 Follow-Up on AEs

All non-serious AEs should be followed until they are either resolved, i.e., returned to baseline or until the end of the post-treatment FU period (3 weeks after last IMP administration) whichever comes first. AEs meeting one of the serious criteria (including AEs of Special Interest), still ongoing after ending trial participation, should be followed on a regular basis, according to the investigator's clinical judgment, until the event has been resolved or until the investigator can assess it as chronic or stable.

If an ongoing SAE changes in intensity, relationship to IMP or as new information becomes available and/or known for the event, a FU SAE report form should be completed and sent to the sponsor within 24 hours of the change in SAE assessment.

If the investigator becomes aware of an SAE after the long-term FU period with a suspected causal relationship to the IMP, the investigator should report this SAE within the same timelines as for SAEs during the trial.

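### Section 12.4 has no re-treatment period, so toxicity after re-treatment at relapse shares incidence and severity rows with the initial course of up to two cycles

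*Combined protocol and SAP*

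**What the plan says.** **Analysis rule.** Section 12.4 (Safety Analysis) opens the treatment-emergent period and does not close it: "AEs will be regarded as treatment-emergent adverse events (TEAEs) if they occur after first administration of" 131I-omburtamab. For incidence, an AE counts once per patient within system organ class and preferred term. When the same AE recurs, "the occurrence with the highest severity and relationship to IMP will be reported". The section also plans numbers of events beside numbers and percentages of patients, and states: "Adverse event data will be listed individually". The safety analysis set in 12.2 is a single set of everyone dosed.

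**Re-treatment.** The initial course is up to two cycles (7.1). For a CNS/LM relapse during follow-up, 6.1.4 adds that "re-treatment to target minimal residual disease can be considered and allowed in case the patient/parents provide written consent to this". Before such doses "it is recommended that patients undergo the salvage treatment as specified in Appendix 2". Appendix 2 lists resection, craniospinal irradiation and chemotherapy, with stem cell rescue if needed.

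**Endpoint served.** Secondary endpoint 7 (8.1.2) is: "The frequency, type, and duration of treatment-emergent severe adverse events and serious adverse events, including clinically significant laboratory abnormalities".

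**Collection.** Section 10.8 requires SAEs "after the patient has signed the informed consent until 3 weeks after last IMP administration", and afterwards only related SAEs and new cancers. Section 10.9 follows non-serious AEs until they resolve "or until the end of the post-treatment FU period (3 weeks after last IMP administration) whichever comes first". Footnote 18 of Table 1 gives the same 3-week rule. It then adds a calendar cut-off at week 4 (one cycle) or week 8 (two cycles), beyond which only related SAEs and new cancers are reported. It does not mention re-treatment.

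**Deferred detail.** Section 12.1 leaves detail of the analyses to the SAP, whose separate text is not in the document.

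**The concern.** A family, a treating physician or a regulator will first ask what toxicity follows the planned one or two doses. Re-treatment is a different setting: the child has relapsed, has had the drug before, and may just have had more irradiation and chemotherapy. Myelosuppression is an expected risk of the drug (10.7), and the salvage chemotherapy may need stem cell rescue. Section 9.1.2.5 already concedes that late effects of earlier irradiation are hard to tell from CNS toxicity of the drug. If both settings share one row, the planned tables cannot answer the question.

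Two smaller issues follow from the same gap. The calendar cut-off in footnote 18 could lead a site to stop recording non-serious AEs before a re-treatment dose is given. The mandatory 3-week intervals after irradiation and after chemo/immunotherapy are tied to the first dose and to enrollment (6.9.2), so nothing binding fixes how soon after renewed therapy a child may be re-dosed.

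**Working it through.** The plan states no figure on this point, so there is none to reproduce. The check is mainly of the text, with arithmetic for scale.

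**1. Do events after re-treatment become TEAEs?** Yes. They occur after the first administration, and 12.4 has no other condition.

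**2. Does anything separate them?** Sections 12.2 and 12.4 neither censor AEs at re-treatment nor define a re-treatment period. The phrase in 12.4 about summarizing by treatment group does not help, because the trial has one arm and no re-treatment group is defined.

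**3. Does the answer depend on how the collection rules are read?**
- If the last administration includes re-treatment doses (the natural reading of 10.8 and 10.9), all AEs to 3 weeks after those doses are collected, and all are pooled.
- If the week 4/8 cut-off in footnote 18 governs, only related SAEs and new cancers are collected after re-treatment. These are still TEAEs and still pooled.

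Pooling occurs either way. Only the amount differs.

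**4. What does the worst-occurrence rule do?** Take a child with Grade 3 thrombocytopenia in the initial course and Grade 4 after re-treatment, both under one preferred term. The incidence table shows the child once, and the severity summary shows Grade 4. With different preferred terms, both would appear.

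**5. Scale per child.** Section 6.8 plans 32 to 50 patients. A re-treated child whose first event of a given type follows re-treatment raises that row by 1/32 = 3.1 percentage points, or 1/50 = 2.0.

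**6. Illustration, all rates assumed.** Let n = 32, let r children be re-treated, let 30% have Grade 3-4 myelosuppression after the initial course, and let q be the rate after re-treatment among re-treated children with no earlier event. Assume that full AE collection applies and that re-treatment is unrelated to earlier myelosuppression.

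Pooled rate = 0.30 + (r/32) × 0.70 × q

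| r | q | Pooled rate |
|---|---|---|
| 4 | 0.25 | 0.322 |
| 4 | 0.50 | 0.344 |
| 8 | 0.50 | 0.388 |
| 8 | 0.75 | 0.431 |

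The central range is 34-39% and the full range 32-43%, against an unchanged 30% for the initial course. For comparison, the exact (Clopper-Pearson) 95% interval for 10/32 is 16.1% to 50.0%. The shift lies well inside it. If the footnote 18 cut-off governed, non-serious cytopenias after re-treatment would not be collected and the shift would be smaller.

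**7. Precision of a separate re-treatment column.** With no events in r children, the exact two-sided 95% upper limit is 1 − 0.025^(1/r): 60.2% for r = 4 and 36.9% for r = 8.

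**The case against.** The best case for the plan is that a dose at relapse is the same drug in the same trial. Counting later events as treatment-emergent is coherent and conservative. Repeats enter the event counts, a change of severity creates a new AE record (10.6.4), and the individual listings let a reader separate the courses by date. Periods and table columns are ordinary SAP content, and that text is not available. All of this stands, and it is why the pooled column should stay. It does not supply a summary by course, and SAP wording would not repair footnote 18 or 6.1.4, which are protocol text.

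Several stronger readings are tempting, and the documents do not support them:
- **Only one worst event per child is reported.** The rule works per preferred term, for incidence only.
- **Toxicity is hidden or rates are seriously distorted.** Nothing collected is dropped from the counts and listings, and the illustrated shift is below sampling error.
- **Re-treated children are unprotected.** The 6.9.3 criteria carry no time limit. The one-week gap after myelosuppression support (6.1.3) applies to any administration, and blood counts are scheduled in all treatment cycles (11.1). Appendix 2 places irradiation at week -10 and chemotherapy at week -5, both longer than 3 weeks before dosing, though only as advice at the physician's discretion. Figure 2, the re-treatment scheme, is not shown.
- **A split by course would settle causation.** A late effect of the initial course could surface after re-dosing, and an event during renewed salvage could precede re-dosing. The split shows timing only.

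**Conclusion.** The point holds as a reporting gap that is worth closing. On the readable text, the toxicity of the planned one or two doses cannot be read from the planned summaries or from secondary endpoint 7 once any child is re-treated. This rests on three conditions: at least one child is re-treated, AEs are collected after those doses at least to the extent of related SAEs, and the unseen SAP does not already define a re-treatment period.

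The effect on rates is unknown, because the documents give neither the number re-treated nor event rates after re-treatment. It is probably smaller than the sampling error of a trial of 32 to 50 children. A reader might infer that the safety rates are unreliable as they stand, and the documents do not support that. The pooled rate is a valid all-exposure figure, but it answers a different question from the one most readers will bring. The collection conflict in footnote 18 is real but small. The re-dosing intervals are a secondary clarification.

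**What to change.** 1. **Section 12.4.** Present TEAEs in three columns: initial course (events starting before the first re-treatment dose, in the safety set), re-treatment (events from that dose on, among children re-treated), and all exposure (the current pooled count). Apply the worst-occurrence rule per preferred term within each column. Describe this as a split by timing, not attribution, and flag events that start after renewed salvage therapy. Start dates of anti-cancer treatment are already recorded (9.2.7; Table 1, footnote 19).
2. **Table 1, footnote 18.** State that full AE collection restarts at each re-treatment dose and runs for 3 weeks after it. This agrees with 10.8 and 10.9 and removes the conflict with the week 4/8 cut-off.
3. **Section 6.1.4 (secondary).** State that the toxicity criteria in 6.9.3 bar re-treatment, and that the existing 3-week irradiation and chemo/immunotherapy intervals are a minimum before any re-treatment dose. No blood-count threshold stricter than the cycle 2 rule is needed.

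The cost is protocol wording and two extra table columns, with no added patients, visits or blood tests. There are two downsides. The re-treatment column will be small and imprecise, as the zero-event limits above show. A fixed 3-week minimum could briefly delay re-dosing of a relapsed child.

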¹⁰ If CSF sample is positive for abnormal cells or outside reference ranges for any of the following: 1. total protein 2. glucose 3. cell count, it must be repeated within 4 weeks of the sample at screening. If abnormal CSF glucose (CTCAE \geq Grade 2) is obtained, a fasting serum glucose is to be obtained at next patient visit. At week 26, the CSF analysis should include cytology only.

¹¹ Treatment with potassium iodide and Cytomel should be initiated 1 week prior to each ¹³¹I- omburtamab infusion in a cycle and continue until 2 weeks after ¹³¹I- omburtamab infusion in the same cycle..

¹² Thyroid protection should be initiated 1 week prior to IMP administration. See section 7.2.5 for further details.

¹³ Thyroid protection should be initiated 1 week prior to next IMP administration – this is only applicable for week 4 and not week 8. See section 7.2.5 for further details.

¹⁴ Beginning 24 hours before ¹³¹I-omburtamab administration please see section 6.1.2.

¹⁵ Given 1-2 hours prior to ¹³¹I-omburtamab administration, including oral acetaminophen/paracetamol and antihistamine (e.g., diphenhydramine), please see section 6.1.2¹⁶
Drawn and held for culture if elevated body temperature after dosing suggests infection rather than expected response to intracerebroventricular dosing.

¹⁷ Dose reduction: 50% (25 mCi) for patients < 1 of age and 33% (33.5 mCi) for patients age 1 year to < 3 years of age, respectively.

¹⁸ Non-SAE's captured from signing the informed consent form (ICF) to dosing should be recorded as medical history. AEs should be reported until 3 weeks after the last IMP administration. SAE's should be captured from signing the ICF. Starting at week 4 (for patients receiving only one cycle) and starting at week 8 (for patients receiving both cycles) only SAEs considered related to ¹³¹I-omburtamab or new onset of cancers regardless of causality should be reported.

¹⁹ Limit to therapy related to cancer.

²⁰ In case fertile women (experienced menarche prior to screening or during treatment, until week 8) are enrolled; pregnancy testing should take place at screening, at week 4 and week 8, and at follow-up at week 26.

²¹ Follow-up at week 26 (24-29 weeks after first treatment) and Long-term follow-up visits at Weeks 52, 78, 104, 130 & 156 (\pm 4 weeks) can be done at referral site.

²² If done at referral site imaging parameters as required in the Imaging Manual should be followed to the extent possible.

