Before signing the Informed Consent, the patient/parents must be given sufficient time to consider the possible participation. Further, each patient must be informed about their right to withdraw from the trial at any time. Parents and patients will also be informed that research participation is voluntary but if they withdraw from the trial, their data will still be used. When the informed consent form has been signed, the patient/parent(s) receives a copy of the signed form and the original is retained in the investigator site file. A second copy may be kept in the patient's medical notes. The informed consent forms must be signed and dated both by the signee and by the person providing the information to the patient/parents. It is recommended to notify the participant's family doctor of the participant's consent to participate in the trial.

13.4 Special considerations for patients having the Ommaya reservoir implanted at the referring hospital or locally but before entering the screening period.

The Ommaya reservoir is to be placed after the written informed consent has been obtained. In cases where placing of the Ommaya is considered in association with the surgical procedure that is recommended before enrollment in the trial, informed consent may be obtained up to three months before the start of the screening period. This is considered acceptable since placing of the Ommaya in association with the anesthesia induced for the surgical resection of the tumor will reduce the burden to the patient by avoiding an extra surgical procedure. Furthermore, the patient may receive high dose chemotherapy in the period leading up to the screening period which may be associated with myelosuppression and therefore rendering an invasive procedure like Ommaya placement not feasible.

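### The SAE summary in section 12.4 has no treatment-emergent limit, so it can count salvage-therapy events that occurred before the first dose

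*Combined protocol and SAP*

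**What the plan says.** Section 12.4 sets the time limit first: "AEs will be regarded as treatment-emergent adverse events (TEAEs) if they occur after first administration of" the study drug. It then names four summaries: "All TEAEs, ADRs, SAEs and serious adverse reactions (SARs) will be summarized". Only the first carries the limit. A further breakdown follows, "TEAEs will also be summarized by severity and by relationship to IMP", but none by seriousness, so no treatment-emergent SAE table is named. Secondary endpoint 7 (section 8.1.2) is "The frequency, type, and duration of treatment-emergent severe adverse events and serious adverse events".

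On collection, footnote 18 to Table 1 says "SAE's should be captured from signing the ICF", while section 10.8 says "SAEs must be reported from the first trial related activity after the patient has signed the informed consent". Both precede dosing. Footnote 18 sends only non-serious pre-dose events to medical history.

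On timing of consent, section 13.4 provides that, when the device is placed during the recommended tumor surgery, "informed consent may be obtained up to three months before the start of the screening period". It also expects that "the patient may receive high dose chemotherapy in the period leading up to the screening period". Appendix 2 lists the recommended salvage steps from resection at week -12 to a chemotherapy block at week -5.

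**The concern.** Under footnote 18, non-serious events before dosing leave the AE data and serious ones stay. Those serious events then reach a summary that has no dosing cut-off. The safety analysis set (section 12.2) does not help: it removes children who were never dosed, not pre-dose events in children who were.

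This matters for three reasons. SAE frequency is a stated secondary endpoint. The trial has no concurrent control, so a reader cannot subtract background toxicity. The two sources also overlap in kind: section 10.7 lists neutropenia and transfusion-requiring myelosuppression as drug risks, and section 13.4 names myelosuppression as an effect of the preceding chemotherapy. Section 12.4 counts each preferred term once per patient and reports the occurrence of highest severity. Applied to SAEs, that rule could let a severe pre-dose event stand in for a milder post-dose one.

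The length of pre-dose observation also depends on when the device was placed, so children contribute unequal time.

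**Working it through.** The plan gives no figure to reproduce here. The check is date arithmetic followed by an illustration.

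**Pre-dose SAE collection**

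- Ceiling: three months before screening (section 13.4) plus the 30-day screening period (section 6.1.1): 91 + 30 = about 121 days.
- Appendix 2 calendar, consent at resection in week -12: 12 × 7 = 84 days.
- No early consent: at most 30 days.

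The last Appendix 2 chemotherapy block starts at week -5, or 5 × 7 = 35 days before dosing. On that calendar every salvage step starts before the 30-day screening period opens. Early-consent children therefore have the whole salvage sequence inside SAE collection. Other children have at most its later complications.

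**All-cause post-dose SAE collection** (to 3 weeks after the last dose)

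- One cycle: 21 days.
- Two cycles, nominal: 28 + 21 = 49 days.
- Two cycles with the 8-week delay allowed in section 6.1.4: 49 + 56 = 105 days.

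**Ratio of pre-dose to post-dose days**

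| Pre-dose days | One cycle (21) | Two cycles (49) | Two cycles, delayed (105) |
|---|---|---|---|
| 84 | 4.0 | 1.7 | 0.8 |
| 121 | 5.8 | 2.5 | 1.2 |
| 30 | 1.4 | 0.6 | 0.3 |

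These ratios leave out the related SAEs and new cancers that are collected through the 3-year follow-up.

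**Effect on the proportion with an SAE**

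Let *d* be the proportion with a post-dose SAE, *f* the share consenting early, and *q* the proportion of those with a pre-dose SAE. Take pre- and post-dose SAEs as independent and ignore pre-dose SAEs in the other children. The all-SAE proportion is then f × [1 − (1 − q)(1 − d)] + (1 − f) × d, and its excess over *d* is f × q × (1 − d).

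The documents give none of *d*, *f* or *q*. All values below are assumptions, with *d* = 30% and 32 children:

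- f = 25%, q = 20%: excess 0.25 × 0.20 × 0.70 = 3.5 points; total 33.5%; 1.1 children.
- f = 50%, q = 40%: excess 0.50 × 0.40 × 0.70 = 14 points; total 44%; 4.5 children.
- f = 100%, q = 60%: excess 1.00 × 0.60 × 0.70 = 42 points; total 72%; 13.4 children.

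The range shows that the size is open; it is not an estimate.

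**The case against.** The strongest reply is that the endpoint is probably already right. In endpoint 7 the natural reading applies treatment-emergent to both nouns, and the list in section 12.4 follows directly after the TEAE definition, so a statistician might program it that way. Section 12.1 also defers detail to a SAP, and no separate text is available to show whether the SAE table is restricted there. This lowers the likelihood of harm, but section 12.4 taken literally still gives an unrestricted table. On the natural reading of endpoint 7, the two sections disagree.

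A reader might infer that drug toxicity cannot be separated from salvage toxicity. The documents do not support that. Serious adverse reactions have their own summary, TEAEs are split by relationship, and all AEs are listed. A pre-dose event should not be judged related, so only the all-cause SAE table is exposed.

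A reader might also infer that about four months of pre-dose events is typical. It is a ceiling. It needs consent at the earliest permitted date, and early consent applies only when the device is placed at resection. Appendix 2 is itself a recommendation left to the treating physician.

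Other text narrows what counts. Admissions planned before inclusion are not serious (section 10.2), though unplanned complications are not exempted. Neurologic abnormalities present before infusion go to medical history (sections 6.1.3 and 9.2.10), though neither section expressly cancels SAE reporting. Section 10.8 sends AEs between screening and first treatment to medical history without excepting SAEs, which conflicts with footnote 18 and with its own SAE rule. Even read broadly, that sentence does not reach events between early consent and the start of screening, where the Appendix 2 steps begin.

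Finally, an all-SAE table is a legitimate full account of what was collected. That stands; the fault is in having it as the only SAE summary named.

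**Conclusion.** The point holds for the all-cause SAE table. As written, section 12.4 lets that table include unplanned SAEs from resection, irradiation and chemotherapy in dosed children who consented early. Pre-dose collection for them is about 84 days on the Appendix 2 calendar and at most about 121, against at most 30 for the others. If treatment-emergent governs both terms in endpoint 7, the table does not deliver that endpoint.

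The serious adverse reaction table is not materially affected, provided pre-dose events are judged unrelated. No hypothesis test or decision rule in section 12.4 depends on the SAE rate. It would go too far to say that the rate will be inflated by a particular number of children or percentage points: the share consenting early and the SAE rates before and after dosing do not appear in the documents.

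**What to change.** - In section 12.4, make the main SAE summary treatment-emergent SAEs, with onset at or after the start of the first infusion, and word endpoint 7 so that the limit plainly covers SAEs.
- Tabulate pre-dose SAEs separately, with the number of children observed and their days of pre-dose collection.
- Reconcile footnote 18 with section 10.8 on two matters: when SAE collection starts (signature, or first trial activity after it), and whether pre-dose SAEs stay as SAEs or go to medical history.

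The cost is a wording change and one extra table. No new data are needed, since collection already starts before dosing.
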